## **Part B: Intralipid vs ClinOleic**

### **Primary Objective**

To evaluate metabolic, nutritional, infectious and inflammatory parameters in patients receiving SO-based lipid emulsion compared to those of patients receiving OO -based lipid emulsion.

- Primary Outcome: length of stay
- Secondary Outcomes: mortality, nutritional parameters (anthropometry, handgrip-strength, mid-arm circumference, , pre-albumin), inflammation (high sensitivity C-reactive protein; hs-CRP), documented infections, ICU stay, antibiotic-days, liver enzymes, essential fatty acid status

### **Study design**

This is a prospective study that will evaluate the indications of parenteral nutrition in an inpatient setting. As part of their PN prescription, patients will receive either standard lipid (Intralipid) or OO-based lipid emulsion (ClinOleic), alternately depending on their time point of PN start, i.e. one person will receive Intralipid, the next one ClinOleic, etc. We will collect information from patients that have started with parenteral nutrition during their hospitalization and that are hospitalized in medical, surgical or ICU wards. We will also collect retrospective data of 100 patients to compare if the actions of the nutrition team and results change with respect to the prospective data.

Inclusion Criteria:

- Patients 18 years or older

- Patients that are expected to require PN for 5 days or more during their hospitalization
- Patients hospitalized in medical, surgical or ICU wards
- Signed informed consent either from the patient, their legally authorized representative or a direct family member

Exclusion Criteria:

- Patients without PN during their hospitalization

**Part A:** Patients will be approached when they start with PN during their hospitalization and will be followed until their last day of PN or, if occurred before PN ends, death. **Part**

**B:** For the proposed study, we will start PN as usual, according to the patients needs. We will randomly assign patients to receive either Intralipid or ClinOleic as the lipid emulsion in the PN. The amount of calories from the lipid emulsion will be equivalent.

Patients will be followed for one week after their last day on PN and, in addition, major outcomes such as mortality and length of stay will be assessed during the entire hospitalization.

Information regarding the patients nutrition will be obtained from the hospital chart and by direct communication with the PN team (dietitian, nurse, pharmacist) after signed informed consent.

We will analyze the nutritional indications and laboratory results of patients hospitalized in different units who are starting with PN alone or in combination with enteral or oral feeding twice a week. We will use a registry to enter the data.

Measurements: :**Part A** 1) Patient demography: age, sex; 2) Type of patient: medical, surgical and/or ICU patients; 3) Type of any surgery the patient has during hospitalization; 4) Primary indications related to parenteral nutrition, comorbidities, updated CCI (31,32); 5) Nutritional assessment: weight, height, BMI, SGA, estimated energy and protein requirements; 6) comparison of energy received as a goal vs calculated energy requirements using published equations; 7) Energy, dextrose, aminoacids and lipids received by PN.

Total energy and proteins received including enteral nutrition and oral intake. Energy provided by Propofol, if received. In case of enteral nutrition, name and amount of product used; 8) Type of line used (peripheral or central); 9) Vascular access; 10) Reason for ending PN; 11) Number of times and reasons for interruption of PN; 12) Weekly PN related laboratory results; 13) Complications secondary to PN; 14) Outcome of patient

**Part B:** We will include the same measurements as in part A, but will add some additional nutritional parameters which will be done at baseline (Day 0) and after 10 days (Day 10)

with PN. Baseline or day 0 assessments to be done prior to or within 24 hours of PN initiation. Day 10 measurements to be done on day 10 of PN administration. If the PN ends before day 10, we will consider a cutoff at day 7 of PN. This means that if the PN ends before day 7, we will not repeat the measurements or blood work. If PN ends between days 7-9 we will repeat the measurements instead of doing them on day 10 for this special cases.

The parameters to measure will be: hand grip strength (kg), mid arm circumference (cm), SGA and weight as measures of nutritional status. We will also add hs-CRP, pre-albumin, and fatty acid profile in red blood cells (RBC) and plasma to the laboratory results at both time points. Clinical outcomes (documented infections, antibiotic-days or other adverse events) will be monitored for one week post-PN. In addition, mortality and length of stay will be documented for the entire hospitalization.

There are numerous studies that try to elucidate which equation is the best to estimate the energy requirements of hospitalized and healthy people, but none have shown to be comparable to indirect calorimetry, which is considered the gold-standard. The ASPEN guidelines refer to the non-obese critically ill patient and suggest using 25 kcal/kg actual body weight per day, published equations, or to measure energy requirements using indirect calorimetry (35). Moreover, the ESPEN guidelines also suggest prescribing 25 kcal/kg in the ICU population increasing to target over the next 2-3 days (36). In the case of obese critically ill patients, ASPEN guidelines suggest a hypocaloric feeding and they mention that the goal of the enteral nutrition regimen should not exceed 60-70% of target energy requirements, 11-14 kcal/kg actual body weight per day or 22-25 kcal/kg ideal body weight (35). Recently published studies have found that the Penn State equation can be used in patients with mechanical ventilation and that the Penn State modified can be used in older obese patients with mechanical ventilation (37-40).

For non-Icu population, ASPEN and ESPEN guidelines agree in using weight based formulas to calculate energy requirements. The estimated energy requirements should be between 20-40 kcal/kg, depending on the pathology (41-45). At the same time, both guidelines suggest using ideal body weight (IBW) in case of obesity and ESPEN adds ascites as another condition were IBW should be used (35,42,45). For the calculation of IBW we will use Hamwi's equation (46). We will use Penn State formula for ICU ventilated patients and weight based formulas for all other patient populations. Ideal body weight will be used in patients with ascites, obesity or in cases of edema were body weight with edema is much more than usual body weight or body weight at admission. Actual body weight will be used for undernourished or normal weight population.

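### The named lipid is part of the PN order and no masking is described, so length of stay, documented infections, antibiotic-days and grip strength are open to bias of unknown size.

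*Combined protocol and SAP*

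**What the plan says.** Study design makes the product part of the order: "As part of their PN prescription, patients will receive either standard lipid (Intralipid) or OO-based lipid emulsion (ClinOleic"). It describes assignment in two ways. One is strict alternation, "one person will receive Intralipid, the next one ClinOleic, etc"; the other is "We will randomly assign patients to receive either Intralipid or ClinOleic as the lipid emulsion in the PN". Feasibility and Sample Size repeats the alternation, one-to-one, with 150 patients per lipid.

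On data sources, Study design says: "Information regarding the patients nutrition will be obtained from the hospital chart and by direct communication with the PN team (dietitian, nurse, pharmacist"). The Measurements paragraph in the same section records "Energy, dextrose, aminoacids and lipids received by PN" in Part A, and Part B repeats the Part A measurements. Part B adds "hand grip strength (kg), mid arm circumference (cm), SGA and weight as measures of nutritional status". On clinical events it says: "Clinical outcomes (documented infections, antibiotic-days or other adverse events) will be monitored for one week post-PN".

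The Part B objectives make length of stay the primary outcome. The secondary outcomes include grip strength, mid-arm circumference, documented infections, ICU stay, antibiotic-days, mortality, hs-CRP, pre-albumin, liver enzymes and essential fatty acid status. SGA is measured in Part B but appears neither in that outcome list nor among the changes to be compared under Statistical analysis.

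Nothing in the text available for review mentions blinding, open label, coded or covered bags, masked assessors, adjudication of infections or criteria for discharge. It also does not say who tests grip, grades SGA, classifies infections or decides discharge.

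**The concern.** A named product in the order and chart is visible to anyone who reads them, and nothing in the plan keeps those readers away from outcome assessment. Several Part B outcomes depend on judgement or effort. Length of stay ends with a discharge decision. Documented infections and antibiotic-days depend on who is investigated and treated. Grip strength depends on effort and encouragement. SGA is subjective by its own name.

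Expectation could also have a direction. The Background says soybean oil may promote inflammation and that patients on alternative emulsions may do better.

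At stake is whether a difference in these outcomes, or the lack of one, can be attributed to the lipid. Bias of this kind arises after assignment, so sound randomisation alone does not prevent it. The planned t-tests or Mann-Whitney tests, and models adjusting for age, BMI and Charlson index, can neither detect nor remove it.

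**Working it through.** **1. Inputs.** Feasibility and Sample Size gives 150 per group, power 0.8, alpha 0.05, and a cited fish-oil study with mean stay 15 (SD 5) against 17 (SD 8) days. Statistical analysis makes all tests two-sided at 0.05. The documents give no figure for bias from unmasked conduct, so the shifts below are assumptions. SDs of 10 and 15 are also assumptions, used to show the range.

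**2. The plan's own figure.** Common SD = √((5² + 8²)/2) = √44.5 = 6.67. For a 2-day difference, n per group = 2 × (1.960 + 0.842)² × 44.5 / 2² ≈ 175 (176 by the t-test), not 150. With 150 per group the t-test power is 73.5%; 80% would need an SD of about 6.18. This mismatch is a separate matter. It is shown only because 150 and 6.67 are used next.

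**3. Precision of the comparison.** SE of the difference = SD × √(2/150):
- SD 6.67: 0.770 day
- SD 10: 1.155 days
- SD 15: 1.732 days

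At SD 6.67 the smallest significant observed difference is about 1.97 × 0.770 ≈ 1.5 days.

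**4. False-positive rate with no true effect and a spurious shift b.** The rejection probability comes from the noncentral t distribution with 298 degrees of freedom and noncentrality b/SE. For example, b = 1 and SD 6.67 give 1/0.770 = 1.30 and a rate of 25.3%.

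| Assumed shift | SD 6.67 | SD 10 (assumed) | SD 15 (assumed) |
|---|---|---|---|
| none | 5% | 5% | 5% |
| 0.5 day | 9.9% | 7.2% | 6.0% |
| 1 day | 25.3% | 13.9% | 8.9% |

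Half a day is 0.5/17 = 3% of a 17-day stay; one day is 6%.

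**5. The opposite direction.** If the true effect is 2 days and a spurious shift works against it at SD 6.67, the net difference is 1.5 days for a half-day shift (power about 49%) and 1 day for a one-day shift (about 25%), against 73.5% with no shift.

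**6. Which outcomes are exposed.** Length of stay, documented infections, antibiotic-days and grip strength involve a decision or effort by someone who may know the lipid. Mortality and the laboratory measures (hs-CRP, pre-albumin, liver enzymes, fatty acids) leave little room for that.

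**The case against.** The strongest reply is that the protocol is silent on masking and does not declare the trial open label. That point stands. A reader might infer that discharge staff and assessors do know the lipid, but the documents neither identify those people nor say how bags are labelled. They support only that such people can know it.

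Three other tempting inferences also go too far.

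- **Outcome data come from the PN team.** What is obtained "by direct communication with the PN team (dietitian, nurse, pharmacist") is information on the patient's nutrition. No text says this team supplies or judges length of stay, infections or grip, or has a role in discharge.
- **Bias could produce or conceal the whole 2-day difference.** Two days is the difference in the cited fish-oil study. Nothing in the documents shows a bias of that size, and at SDs of 10 or 15 a half-day shift barely moves the error rate. The illustration also models only the t-test, while the plan allows Mann-Whitney.
- **Staff are primed against soybean oil.** The Background also says standard soybean emulsions meet most PN patients' needs and that further research is required. Nothing shows that ward staff read it.

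A fair objection to masking itself is that relabelled bags achieve little under alternation, because one known assignment reveals the others, and that the pharmacist, named as part of the PN team, must hold the code. Both points stand, and the proposed change allows for them. None of these replies supplies the missing masking.

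**Conclusion.** The point holds in this limited form: the lipid is named in the order, no masking is described, and the plan followed as written leaves length of stay, documented infections, antibiotic-days and grip strength open to performance and detection bias of unknown size. SGA is exposed in the same way, but it is a measurement and not a listed outcome.

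The rates in the working illustrate how sensitive the comparison is; they do not estimate the bias. They assume a constant shift in mean stay, a t-test at 150 per group and, for two of the three columns, SDs that are not in the documents. At the plan's own SDs a half-day shift about doubles the 5% error rate, so modest distortion matters. With a larger spread in stay it matters much less. The change is worth making because it is cheap, not because a false result has been shown to be likely.

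**What to change.** 1. Have the order and chart read 'study lipid' at the prescribed lipid calories, which Study design already makes equivalent between arms. Pharmacy dispenses either emulsion under a neutral label and holds the code for urgent clinical need.
2. Replace alternation with a concealed random list. This also settles the two conflicting descriptions of assignment.
3. Keep the lipid name out of the registry fields seen by those who measure grip strength, arm circumference and SGA and those who classify infections.
4. State in the protocol who is masked, who assesses each outcome and how infections are classified. The dispensing pharmacist stays unmasked and should not assess outcomes.

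The cost is a label template, a random list held by pharmacy, a restricted registry field and a small dispensing effort.

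If masking the bags is impractical, hide the lipid field from existing assessors and infection classifiers wherever they do not otherwise know the product, and report length of stay as an unmasked outcome. This fallback does not protect the primary outcome, and it fails for any assessor who sees the bag.

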There is an increasing need for hospitals to do quality-assurance studies for in-patient PN to assess indications, PN prescription, complications, clinical outcomes and costs. The only in-patient population that is well studied is the intensive care unit (ICU) population. Several meta-analyses showed that PN was associated with higher infection rate, longer length of stay and higher mortality when compared with enteral nutrition (12,13). Results from these and other studies were the basis for the Canadian ICU Guidelines (13-17).

The aims of this study (already approved CAPCR 12/5174/AE) ) were to determine if PN prescribed in in-patients follows existing guidelines in terms of timing of nutrition support, prescription and monitoring and, whether it is associated with complications. In addition, clinical outcomes such as length of stay and mortality are assessed.

In addition, we will evaluate, in this cohort of patients, the effect of 2 different lipid emulsions, both approved by Health Canada (Intralipid based on soybean oil and ClinOleic based on olive oil). These lipid emulsions, readily available through our provider, will be prescribed alternatively according to standards of care. We also plan to do additional measurements relevant to nutrition which include: C-reactive protein [CRP], pre-albumin, subjective global assessment, hand grip strength and arm circumference at beginning and 10 days of PN (or at discontinuation if less than 10days). We will also monitor diagnoses of infections during PN, including 1 week after PN discontinuation if patients remain in hospital. We were advised to re-submit as a new study rather than as an amendment.

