## **Statistical analysis**

**Part A:** Descriptive statistics will be performed. Results will be expressed as absolute numbers and percentages, mean  $\pm$  standard deviation (SD) or median (minimum; maximum) depending on the variable types and distributions, separately for the prospective and the retrospective dataset.

For the prospective study, multivariate logistic regression will be performed to identify risk factors associated with specific PN prescription: for example, inadequate administration of PN. In addition, data from the prospective study and the retrospective chart review will be compared by unpaired t-test, Mann-Whitney-test or chi-square test as appropriate. A p value  $<0.05$  will be considered statistically significant. **Part**

**B:** For the Intralipid and the ClinOleic analysis, all variables will be tested for normal distribution (Shapiro Wilks test). *Primary outcome* is length of stay (in days). The Intralipid and ClinOleic groups will initially be compared with unpaired t-test or Mann-Whitney test as appropriate. *Secondary outcomes*: other clinical outcomes (days in ICU, antibiotic-days, infections, mortality) will also be analyzed the same way initially. For secondary outcomes that may change over time, i.e. hs-CRP, pre-albumin and other laboratory results, BMI, arm circumference, hand grip strength, changes will be compared between groups using unpaired t-test or Mann-Whitney test as appropriate. To account for possible covariate effects (eg. age, baseline BMI, Charlson comorbidity index), regression methods such as generalized linear models will be employed. All tests will be based on two-sided alternatives and a test will be considered statistically significant using alpha=0.05. SAS Enterprise Guide 4.1 software (SAS Institute Inc., Cary, NC, USA) will be used.

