## **Feasibility and Sample Size**

**Part A:** Based on previous studies, there are about 200 in-patients per year receiving PN. All patients will be assessed as per standard medical guidelines for PN and it is expected that 90% will agree to participate in the project. We calculate that we will have enrolled about 50 patients for Part A, before we start with part B. We will later include 150 more patients from Part B to have a total of 200 patients. We will compare the data obtained with 100 retrospective patients to see if the actions of the nutrition team changed since we started the project.

**Part B:** When we receive the ClinOleic in the hospital, patients will receive either SO-based lipid emulsion (Intralipid= 150 patients) or OO-based lipid emulsion (ClinOleic=150 patients) on an alternate basis (one-to-one) for the duration of the PN.

The total number of patients including part A and part B is estimated to be 350 patients. It is expected to take about one and a half years to recruit this number of patients.

For the Intralipid and ClinOleic analysis, we based our sample size on a study that evaluated the use of either SO or SO + fish oil (FO) in 206 patients with gastrointestinal or colonic cancer during 7 days after surgery and found that the patients that were given the FO treatment had significantly shorter length of stay than the SO group (Mean (SD) 15(5) versus 17(8) p= 0.041). Also, they had fewer infectious complications (50). Another study compared soybean oil and soybean oil+FO in 57 elderly patients with colorectal cancer. In the treatment group, there were fewer infectious complications and incidences of systemic inflammatory response syndrome (SIRS), and shorter lengths of hospital stay were observed(51).

Based on this, we estimate that a sample size of 150 in each group with a power of 0.8 and alpha of 0.05 will be sufficient to show a similar difference in length of stay between the two groups (soybean or ClinOleic) using the online sample size calculation provided by G.W. Snedecor & W.G. Cochran  
<http://www.biomath.info/power/ttest.htm>.

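### Part B is called random in one place but is specified as strict alternation, with no concealment described, so the next lipid can be known before a patient is enrolled

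*Combined protocol and SAP*

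**What the plan says.** Allocation is described in four places.

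- **Study design, opening paragraph:** patients receive one or other lipid "alternately depending on their time point of PN start, i.e. one person will receive Intralipid, the next one ClinOleic, etc".
- **Study design, Part B:** "We will randomly assign patients to receive either Intralipid or ClinOleic as the lipid emulsion in the PN". No method is attached to this sentence.
- **Feasibility and Sample Size, Part B:** 150 patients per emulsion, allocated "on an alternate basis (one-to-one) for the duration of the PN".
- **Introduction:** the emulsions "will be prescribed alternatively according to standards of care". This is looser, and may mean only that a patient gets one or the other.

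Entry to the study depends on two further items in the inclusion criteria: "Patients that are expected to require PN for 5 days or more during their hospitalization" and "Signed informed consent either from the patient, their legally authorized representative or a direct family member". Under Part B the plan also says "we will start PN as usual, according to the patients needs". The supplied text does not say how a sequence is produced, who holds it, whether it is hidden from those who enrol, or whether anyone is blinded. It does not state the order in which eligibility, consent and lipid assignment take place.

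**The concern.** Random assignment and one-after-the-other alternation cannot both be true. Alternation is the only method the plan spells out, so the plan claims a property that its procedure lacks.

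The practical risk is selective enrolment. Whether PN is likely to last five days or more is a judgement. Consent depends on how and whether a patient or family is approached. If the person making that judgement or approach knows which lipid comes next, the two groups can come to differ in prognosis without any bad faith. Expected PN duration is plausibly related to length of stay, so the primary comparison is exposed, as are the secondary ones. A larger sample does not remove such a bias. The Statistical analysis section plans regression, "To account for possible covariate effects (eg. age, baseline BMI, Charlson comorbidity index), regression methods such as generalized linear models will be employed", but adjustment can deal only with factors that were measured.

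**Working it through.** The plan gives no figure on this point, so the check sets the statements side by side and then adds an illustration of scale.

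**1. Which method is specified?** Two statements clearly describe alternation (the opening of Study design; Feasibility and Sample Size, Part B), and the second applies it to Part B explicitly. One statement says random and gives no mechanism. The Introduction is ambiguous and is not needed for the conclusion.

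**2. How predictable is the next assignment?**

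| Method | Assignments guessed correctly from past ones |
|---|---|
| Strict alternation | 100% |
| Permuted blocks of 4 and 6 (simulated, guessing the arm that is behind) | about 69% |
| Simple randomisation | 50% |

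**3. Can the knowledge act before enrolment is settled?** There are two possible orders.

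- Consent first, lipid second: the lipid can be predicted from the previous patient while eligibility and consent are still open.
- Lipid first with routine PN, consent second: the lipid is already known when consent is sought.

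Both leave room for selection. It is also unclear whether the alternation counts every patient starting PN or only those who consent.

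**4. Illustration of scale (the bias sizes are assumed).**

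Inputs from Feasibility and Sample Size: SDs of 5 and 8 days, means of 15 and 17 (target difference 2 days), 150 per group. Two-sided alpha of 0.05 is from Statistical analysis.

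- Pooled SD = √((5² + 8²)/2) = √44.5 = 6.671
- SE = 6.671 × √(2/150) = 0.770
- With no true effect and bias b, the rejection rate is 1 − Φ(1.96 − b/SE) + Φ(−1.96 − b/SE)

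The plan recruits from medical, surgical and ICU wards, so a wider SD is also shown. It assumes a 10-day gap in stay between ICU and other patients and a 30% ICU share, neither of which is in the documents: √(44.5 + 0.3 × 0.7 × 10²) = √65.5 = 8.09, so SE = 8.09 × √(2/150) ≈ 0.93.

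| Assumed bias (days) | Share of 2-day target | Rate, SD 6.67 | Rate, SD 8.09 |
|---|---|---|---|
| 0.25 | 12.5% | 0.062 | 0.058 |
| 0.5 | 25% | 0.099 | 0.083 |
| 1.0 | 50% | 0.255 | 0.188 |

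**5. How large could the bias be through refusal alone?** Feasibility and Sample Size expects 90% to agree (stated under Part A). Suppose selection acts only through the missing 10%, and in one arm only.

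- If the enrolled 90% have a mean b below that arm's overall mean, the missing 10% must lie 0.9b/0.1 = 9b above it: 2.25, 4.5 or 9 days for the three biases.
- Removing exactly the longest-staying 10% of a normal distribution with SD 6.67 shifts the mean by (0.1 × 1.755/0.9) × 6.67 = 1.3 days, which is the ceiling for that route in one arm.

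The 1.0-day case is therefore near the extreme for refusal in one arm. Opposite selection in the two arms would double the ceiling to 2.6 days. Selection through the five-day judgement would come on top and cannot be quantified from the documents.

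**The case against.** The strongest defence is that the plan has one concrete mechanism, 1:1 alternation by PN start, and that *randomly* is a loose label for it. On that reading only a word needs correcting. Several features also limit selection. PN starts on clinical need, not at a recruiter's choice. Patients are approached when PN starts (stated under Part A). Part B baseline assessments must be done before, or within 24 hours of, PN initiation. Some 90% are expected to agree. The documents do not say who knows the previous assignment. Finally, the false-positive rates only translate an assumed bias; nothing in the plan links alternation to any particular number of days.

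Much of this is fair. The short window makes selection on the later hospital course unlikely, and high participation limits selection through refusal. The rates are no evidence that bias will occur. But a narrow window does not hide the next lipid, and the five-day judgement and the consent approach both fall within it. If only the label is wrong, correcting it still changes what the trial may claim, because a quasi-randomised comparison has to be read with this limitation stated.

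**Conclusion.** The concern holds. The plan contradicts itself on how Part B patients are allocated. The method it actually specifies is fully predictable to anyone who knows the previous assignment, and no safeguard is described in the supplied text. This must be fixed, because allocation cannot be repaired after patients are enrolled.

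The conclusion rests on the contradiction and the missing concealment, not on the illustrative rates. The finding is a risk of selection bias in length of stay and the secondary outcomes; it is not a demonstration that bias occurs. Its size is unknown. The 6% to 25% range depends on assumed biases of 0.25 to 1.0 day, SD 6.67, 150 per group and a normal approximation.

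**What to change.** 1. Replace alternation with a computer-generated 1:1 list using random block sizes. It should be held by someone who neither judges eligibility nor takes consent, such as a pharmacist or statistician, and kept from those who enrol. Blocks leave some predictability where past assignments are known (about 69% in the simulation above), so concealment is needed as well; simple randomisation avoids this at the price of possible unequal group sizes.
2. Release each assignment only after eligibility and consent are recorded. State that order, and state which patients the sequence counts.
3. Make Study design and Feasibility and Sample Size agree with this, and clear up the wording in the Introduction.
4. If alternation is kept, or any patients have already been allocated that way, remove the statement of random assignment for them and report the allocation as quasi-randomised, with the limitation stated.

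The cost is a generated list, an independent holder and an amendment of a few sentences. The real drawback is timing: the lipid cannot be assigned until consent is recorded, which may take a while when a representative must sign. The plan has to reconcile that with its statement that PN starts as usual; how to do so clinically is for the investigators.
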